APPENDIX 4. CLASSIFICATION OF TREATMENT OUTCOMES⁷

Early treatment failure

- danger signs or severe malaria on day 1, 2 or 3 in the presence of parasitaemia;
- parasitaemia on day 2 higher than on day 0, irrespective of axillary temperature;
- parasitaemia on day 3 with axillary temperature ≥ 37.5 °C;
- parasitaemia on day 3 $\geq 25\%$ of count on day 0.

Late treatment failure

Late clinical failure

- danger signs or severe malaria in the presence of parasitaemia on any day between day 4 and day 42) in patients who did not previously meet any of the criteria of early treatment failure;
- presence of parasitaemia on any day between day 4 and day 42) with axillary temperature ≥ 37.5 °C (or history of fever) in patients who did not previously meet any of the criteria of early treatment failure

Late parasitological failure

- presence of parasitaemia on any day between day 7 and day 42) with axillary temperature < 37.5 °C in patients who did not previously meet any of the criteria of early treatment failure or late clinical failure

Adequate clinical and parasitological response

- absence of parasitaemia on day 42), irrespective of axillary temperature, in patients who did not previously meet any of the criteria of early treatment failure, late clinical failure or late parasitological failure

⁷ WHO. *Susceptibility of Plasmodium falciparum to antimalarial drugs. Report on global monitoring 1996–2004*. Geneva, World Health Organization, 2005 (WHO/HTM/MAL/2005.110) (<http://www.who.int/malaria/resistance>).

APPENDIX 5. CASE SCREENING FORM

Case screening form	
Health centre name:	Study number:
Locality:	Patient screening number:
District:	Date of visit (dd-mm-yyyy):
Province:	
Demographic data	
Date of birth (dd-mm-yyyy):	or estimated age: in:  months or  years
Height (cm):	Weight (kg):
Sex:  Male  Female	
If female, is the patient pregnant?  Yes  No  Not sure (If yes, patient is not eligible)	
If pregnant, provide the date of the last menstrual period (dd-mm-yyyy):	
Pre-treatment temperature	
History of fever in previous 24 h?  Yes  No	
Temperature: °C  Axillary	
Thick and thin blood smears for estimation of P. falciparum parasite counts	
Species:  P. falciparum  P. vivax  P. ovale  P. malariae	
Were species other than P. falciparum present?  Yes  No (If yes, patient is not eligible).	
Approximate number of P. falciparum asexual parasites:	
Presence of 1–200 parasites / 12 white blood cells?  Yes  No (If no, patient is not eligible)	
Presence of P. falciparum gametocytes?  Yes  No	
Has a blood sample for PCR been collected?  Yes  No	
Haematocrit: %	
Urinary analysis (pregnancy test for female patients)	
Result of pregnancy test:  Positive  Negative (If positive, patient is not eligible)	
Inclusion criteria	

 • age between 2 and 60 years • mono-infection with P. falciparum confirmed by positive blood smear (i.e. no mixed infection) • parasitaemia between 500 and 100,000/μl of asexual forms • measured temperature (depending on method of measurement) or history of fever within previous 24 h • ability to swallow medication 	

 • ability and willingness to comply with the study protocol for the duration of the study and to comply with the study visit schedule • absence of severe malnutrition (defined as per protocol) 	
Does the patient meet all the inclusion criteria?  Yes  No (If no, patient is not eligible)	
Case screening form (page 2)	
Exclusion criteria	

 • signs and symptoms of severe or complicated malaria requiring parenteral treatment according to WHO criteria (Appendix 1) • mixed or mono-infection with another Plasmodium species detected by microscopy • severe malnutrition • febrile conditions caused by diseases other than malaria or other known underlying chronic or severe diseases • regular medication which interferes with antimalarial pharmacokinetics • history of hypersensitivity reactions or contraindications to the medicine tested • positive pregnancy test or breastfeeding • unable to or unwilling to take contraceptives. 	
Does the patient meet any of the exclusion criteria?  Yes  No (If yes, the patient is not eligible)	
If yes, please specify the reason for exclusion:	
Patient informed consent and assent	
Consent form signed:  Yes  No	Patient identity number:
Assent form signed:  Yes  No	Date (dd-mm-yyyy):

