COVER SHEET FOR THERAPEUTIC EFFICACY TEST PROTOCOL

Title	Monitoring and evaluation of the efficacy and safety of Artesunate-Mefloquine (ASMQ) and Artesunate-Pyronaridine (ASP) for the treatment of uncomplicated Plasmodium falciparum and Plasmodium vivax malaria in Cambodia
Study sites	
Site 1: Trapeang Cho Health Center, Kampong Speu district, Kampong Speu province ACT tested: Artesunate-Mefloquine (ASMQ)
 
Site 2: Veunsai Health Center, Veunsai district, Rattanakiri province ACT tested: Artesunate-Pyronaridine (Pyramax)
 
Site 3: Chambak Health Center, Phnom Sruoch district, Kampong Speu province ACT tested: Artesunate-Mefloquine (ASMQ)
 
Site 4: Cheu Tom Health Center, Krakor district, Pursat province ACT tested: Artesunate-Pyronaridine (Pyramax)
 
Site 5: Keo Seima Health Center, Saen Monourom district, Mondulkiri ACT tested: Artesunate-Mefloquine (ASMQ)

Protocol submission date	10/03/2020
Protocol number	Cambodia 1
Principal investigator	
[name]. MD, DrPH., Postdoc National Centre for Parasitology, Entomology and Malaria Control Program, Cambodia Head of Health Research Unit [contact] [contact] Email: [contact]

Co- investigator	
[name]., MD., DrPHS Vice Director National Centre for Parasitology, Entomology and Malaria Control Cambodia [name] [contact] E-mail: [contact]

Co-investigator	
[name] [name], M.D., MTM Malaria Medical Officer World Health Organization [contact] [contact]

Co-investigator	
[name] [name] Antimalarial drug resistance Global malaria Programme World Health Organization [name] [contact] [contact] Email: [contact]

Participating institutions	Institute Pasteur du Cambodge, Phnom Penh [name] [contact] [name]
Study dates	From June to December 2018
Sponsor	Ministry of Health, Cambodia [name] [contact] Office: [name] [contact] [contact] Email: [contact]

SYNOPSIS

Title: Artesunate-Mefloquine (ASMQ) and Artesunate-Pyronaridine (ASP) for the treatment of uncomplicated Plasmodium falciparum and Plasmodium vivax malaria.

Purpose: To assess the efficacy of the current first line treatment policy; To assess the efficacy of a new antimalarial drug to support updating of the national policy.

Study period: June to December 2020

Study Sites:

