3.3 Study population

The study population will consist of patients with uncomplicated *P. falciparum* or *P. vivax* malaria attending the study health clinic who are aged between 2-60 years for ASP and 18-60 years for ASMQ. All adult patients who are above 18 years, age of majority in this country, will sign an informed consent form for participation. Parents or guardians will give informed consent on behalf of children who have not reached the age of majority. Children aged from 12 years and age of majority will be required to consent for participation by signing an informed assent form.

The criteria of the age range included in this surveillance relies on the pattern of malaria infection and their potential involvement in the surveillance study. Those patients under 2 and over 65 are excluded because they may need additional health service support at the higher level while the surveillance study is based at the health centers.

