3.5 Inclusion criteria

- For those receiving ASP: age between 2 and 60 years
- For those receiving ASMQ: age between 18 and 60 years;
- mono-infection with *P. falciparum* or *P. vivax* by microscopy; *P. falciparum* or *P. vivax* parasitaemia of 500-100,000/ μ l asexual forms;
- presence of axillary ≥ 37.5 °C or history of fever during the past 24 h;
- ability to swallow oral [by mouth] medication;
- ability and willingness to comply with the study protocol for the duration of the study and to comply with the study visit schedule; and
- informed consent from the patient or from a parent or guardian in the case of children aged less than 12 years;
- informed assent from any minor participant aged more than 12 years and less than 60 years; and
- consent for pregnancy testing from female of child-bearing potential and from their parent or guardian if under 18 years.

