3.6 Exclusion criteria

- presence of general danger signs in children aged under 5 years or signs of severe falciparum malaria according to the definitions of WHO (Appendix 1);
- Age less than 2 years old and over 60 for ASP, under 18 and over 60 for ASMQ;
- mixed or mono-infection with another *Plasmodium* species detected by microscopy;
- presence of severe malnutrition (defined as a child whose growth standard is below -3 z-score, has symmetrical oedema involving at least the feet or has a mid-upper arm circumference < 115 mm);
- presence of febrile conditions due to diseases other than malaria (e.g. measles, acute lower respiratory tract infection, severe diarrhea with dehydration) or other known underlying chronic or severe diseases (e.g. cardiac, renal and hepatic diseases, HIV/AIDS);
- regular medication, which may interfere with antimalarial pharmacokinetics;
- history of hypersensitivity reactions or contraindications to any of the medicine(s) being tested or used as alternative treatment(s);
- a positive pregnancy test or breastfeeding;
- unable to or unwilling to take pregnancy test or to use contraception for women of child-bearing age (defined as age > 12 years and sexually active).

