3.8 Patient discontinuation or protocol violation

Study patients who meet any of the following criteria will be classified as withdrawn.

- withdrawal of consent. A patient may withdraw consent at any time, without prejudice for further follow-up or treatment at the study site.
- failure to complete treatment, due to:
 - persistent vomiting of the treatment. A patient who vomits the study medication twice will be withdrawn from the study and given rescue treatment.
 - failure to attend the scheduled visits during the first 3 days; or
 - serious adverse events necessitating termination of treatment before the full course is completed. A patient can be discontinued from the study if the principal investigator decides so due to an adverse event of adequate nature or intensity. In this case, information on the adverse event and symptomatic treatment given must be recorded on a case report form. If the adverse event is serious, the principal investigator must notify the sponsor or its designee immediately and follow the reporting procedures described in section 5.3.
- enrolment violation:
 - severe malaria on day 0; or
 - erroneous inclusion of a patient who does not meet the inclusion criteria.
- voluntary protocol violation: self- or third-party administration of antimalarial drug (or antibiotics with antimalarial activity) (Appendix 2);
- involuntary protocol violation:
 - occurrence during follow-up of concomitant disease that would interfere with a clear classification of the treatment outcome;
 - detection of mono-infection with another malaria species during follow-up; or
 - misclassification of a patient due to a laboratory error (parasitaemia), leading to administration of rescue treatment.

Patients who are withdrawn will nevertheless be followed up until recovery or the end of follow-up, if possible; however, no treatment outcome will be assigned to these patients, and they will be censored or excluded from the analysis. The reasons for discontinuation or protocol violation will be recorded on the case report form.

Pregnancy detected during the course of follow-up does not constitute a reason for withdrawal but the event must be recorded and managed as described in section 5.3.

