4. TREATMENT

4.1 Antimalarial treatment

ASMQ (Artesunate + Mefloquine co formulated).

The adult dose tablet contains 100mg Artesunate plus 220mg Mefloquine and the paediatric tablet contain 55mg Artesunate plus 55 mg Mefloquine. (Refer to Annex table for more detailed dosage).

ASP (Artesunate + Pyronaridine/ Pyramax): Adults and children \geq 20 kg (Refer to Annex table for more detailed dosage).

All doses of medicine will be administered under the supervision of a qualified member of the staff designated by the principal investigator. The study patients will be observed for 30 min after medicine administration for adverse reactions or vomiting. Any patient who vomits during this observation period will be re-treated with the same dose of medicine and observed for an additional 30 min. If the patient vomits again, he or she will be withdrawn and offered rescue therapy. The patients are recommended to stay at the health facility until they complete the treatment course for malaria infection.

All doses of medicine will be administered under the supervision of a qualified member of the staff designated by the principal investigator. The study patients will be observed for 30 min after medicine administration for adverse reactions or vomiting. Any patient who vomits during this observation period will be re-treated with the same dose of medicine and observed for an additional 30 min. If the patient vomits again, he or she will be withdrawn and offered rescue therapy. The patients are recommended to stay at the health facility until they complete the treatment course for malaria infection.

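### The Appendix 5 screening form admits ages 2 to 60 for both drugs, contradicting the ASMQ age range of 18 to 60 in the protocol body

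*Protocol*

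**What the plan says.** Section 3.5 sets the age criterion by drug: "For those receiving ASP: age between 2 and 60 years" and "For those receiving ASMQ: age between 18 and 60 years". Section 3.6 repeats it as an exclusion, "under 18 and over 60 for ASMQ". The synopsis and the first sentence of section 3.3 give the same two ranges.

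Appendix 5, the case screening form, has one age line in its inclusion list, "age between 2 and 60 years", with no split by drug or site. Its exclusion list has no age item. Section 6.1 makes this the form for every patient screened, and the form asks whether all inclusion criteria are met directly below its own list.

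Section 3.8 names "erroneous inclusion of a patient who does not meet the inclusion criteria" as an enrolment violation. Such a patient is withdrawn, receives no treatment outcome, and is censored or excluded from the analysis.

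Three other places bear on age:
- Section 3.3 goes on to explain the range with a different upper limit: "Those patients under 2 and over 65 are excluded because they may need additional health service support at the higher level".
- Section 4.1, describing ASMQ, says that "the paediatric tablet contain 55mg Artesunate plus 55 mg Mefloquine".
- The ASMQ chart in Appendix 3 lists the adult tablet only, by weight, with bands of 18-29 kg and 30 kg or more.

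**The concern.** Appendix 5 is the only eligibility checklist in the protocol, and it disagrees with the eligibility rule for one of the two drugs. A ten-year-old presenting at Trapeang Cho, Chambak or Keo Seima satisfies the form's age line and meets no age exclusion, so staff working from the form would record the child as eligible on age. Under sections 3.5 and 3.6 the same child is ineligible.

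Two things are at stake. A minor would be treated with a study drug outside the protocol's own criteria. The patient would then be lost to the efficacy estimate, at a site and for a species where the sample size leaves little slack. The form cannot catch the error, because it tests age against the wrong range.

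The other ASMQ text gives staff no clear signal that the form is wrong. A paediatric tablet and an 18-29 kg band can both be read as expecting children.

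**Working it through.** **1. The age texts side by side**

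| Place | ASMQ | ASP |
|---|---|---|
| Synopsis | 18-60 | 2-60 |
| Section 3.3, first sentence | 18-60 | 2-60 |
| Section 3.3, explanation of the range | excludes under 2 and over 65, no split | same |
| Section 3.5 | 18-60 | 2-60 |
| Section 3.6 | excludes under 18 and over 60 | excludes under 2 and over 60 |
| Appendix 5, inclusion | 2-60, no split | 2-60, no split |
| Appendix 5, exclusion | no age item | no age item |

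The form agrees with the body for ASP and disagrees for ASMQ over ages 2 to 17. The ASMQ chart in Appendix 3 would not reliably stop such a patient: it goes by weight, so any child of 18 kg or more has a row.

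**2. The plan's own sample size**

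Inputs from section 8.1: failure rate p = 0.10, 95% confidence (z = 1.96), precision d = 0.08, allowance 10%.

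n = z² p(1 − p) / d² = 1.96² × 0.09 / 0.0064 = 54.02, stated as 54.

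Allowance: 54 / 0.90 = 60.0, or 54 × 1.10 = 59.4, rounded up to 60. The stated 54 and 60 reproduce. The synopsis total also follows: 5 sites × 2 species × 60 = 600.

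Room for losses per site and species: 60 − 54 = 6. Seven under-18 inclusions with no other loss would leave 53, one below the stated minimum. The half-width would then be 1.96 × √(0.09 / 53) = 8.08%.

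**3. Effect of following the form at an ASMQ site**

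Let f be the share of enrolled ASMQ patients under 18. The documents do not give f, so a range is assumed. The 10% allowance is taken as used up by ordinary losses, as planned.

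- Evaluable patients: E = 60 × 0.90 × (1 − f)
- Half-width: 1.96 × √(0.09 / E)
- Enrolment needed to keep 54 evaluable: 54 / [0.90 × (1 − f)], rounded up

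| Assumed f | Evaluable of 60 | Half-width | Enrolment needed |
|---|---|---|---|
| 0% | 54.0 | 8.0% | 60 |
| 5% | 51.3 | 8.2% | 64 |
| 10% | 48.6 | 8.4% | 67 |
| 20% | 43.2 | 9.0% | 75 |
| 30% | 37.8 | 9.6% | 86 |

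Correcting the form changes none of the plan's stated figures.

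**The case against.** The strongest reply is that the eligibility rule is clear. The ASMQ range is the same in four places in the body, and section 6.1 requires all enrolment criteria to be met before consent is sought. The form also reads like a *P. falciparum* template: it asks for *P. falciparum* mono-infection and marks any other species as ineligible, so no site could follow it literally and still recruit the *P. vivax* patients. On this view staff would work from sections 3.5 and 3.6, and no child would be enrolled on ASMQ. It is fair that the harm is conditional on the form being followed. But a second error in the same checklist does not cure the first, and the form is what gets completed for each patient.

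A second reply is that the loss is modest. Going from 54 to 53 evaluable barely moves the precision, and the guidelines for analysis of results censor a withdrawn patient in the Kaplan-Meier analysis and drop the patient only from the per-protocol proportion. Both points stand and limit the size of the effect.

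A third reply is that the paediatric tablet in section 4.1 is a product description, and that Appendix 3 lists only the adult ASMQ tablet. Neither is an eligibility statement. That is right: these passages need reconciling with the age criterion, but they do not show that children were meant to be enrolled on ASMQ.

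A reader might go further and infer that drug is confounded with age, because ASP is studied from age 2 and ASMQ only in adults. The documents do not support that as a fault. The difference is set openly in sections 3.3 to 3.6, is not caused by the form, and would remain once the form is corrected. The study is described as one-arm, each site tests one drug, and section 8.2 plans no comparison between drugs, so no planned estimate is biased. Reporting ASP separately by age would be a preference, not a correction.

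**Conclusion.** The contradiction is real, and the form is wrong as written for ASMQ. At three of the five sites, following it would admit patients aged 2 to 17 whom section 3.8 then withdraws without an outcome.

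The statistical cost depends on an under-18 share that the documents do not state. Over an assumed 5% to 30%, about 51 to 38 evaluable patients would remain per site and species against the 54 planned, with a half-width of about 8.2% to 9.6% against 8.0%. This rests on staff following the form, on every under-18 inclusion being recognised and withdrawn, and on ordinary losses using the full 10% allowance. If staff apply sections 3.5 and 3.6 instead, nothing is lost.

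Two larger claims should not be read into this. The three ASMQ sites account for 360 of the 600 planned patients (3 × 120), but that is the planned ASMQ total, not the number affected. Nor does an adults-only ASMQ population in itself undermine the stated purpose, "To assess the efficacy of the current first line treatment policy": section 2 already ties the efficacy objective to patients who meet the inclusion criteria, and section 3.5 defines those by drug.

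**What to change.** In Appendix 5, replace the single age line with the two drug-specific lines of section 3.5, and add the age exclusion of section 3.6 to the form's exclusion list.

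Reconcile the age of 65 in section 3.3 with the upper limit of 60 used in the rest of that section, in the synopsis, in 3.5 and 3.6, and on the form. Reconcile the paediatric ASMQ tablet in section 4.1 and the 18-29 kg ASMQ band in Appendix 3 with the ASMQ age criterion. Which of those passages should change is for the investigators to decide.

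The cost is a form correction and a few words of text before enrolment. Sample size, endpoints and analysis are unaffected.

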1- ASMQ: Trapeang Cho, Kampong Speu district, Kampong Speu province; Chambak, Phnom Srouch district, Kampong Speu; Keo Seima, Saen Monourom, Mondulkiri.

2- ASP: Veunsai, Veunsai district, Rattanakiri; Cheu Tom, Krakor district, Pursat

Study Design: This surveillance study is a one arm prospective study

Patient population by treatment regimen:

Artesunate-Mefloquine (ASMQ)

Febrile patients aged between 18 years and 60 years, with confirmed uncomplicated *P. falciparum* and *P. vivax* infections.

Artesunate-Pyronaridine (ASP)

Febrile patients aged between 2 years and 60 years, with confirmed uncomplicated *P. falciparum* and *P. vivax* infections.

Sample Size: 600 (120 in one site: 60 *P. falciparum* cases and 60 patients *P. vivax* cases)

Treatment(s) and follow-up: artesunate-mefloquine (ASMQ) will follow a dosing chart in Annex 3; one tablet of Pyronaridine-Artesunate contains 60mg artesunate+ 180mg pyronaridine; dosing is given based on the weight band (Annex 3). Primaquine will be administered as a single 15-mg adult dose (0.25 mg base/kg).

Clinical and parasitological parameters will be monitored over a 42-day follow-up period to evaluate drug efficacy.

Primary endpoints: The proportion of patients with early treatment failure, late clinical failure, late parasitological failure or an adequate clinical and parasitological response as indicators of efficacy. Recrudescence will be distinguished from re-infection by polymerase chain reaction (PCR) analysis.

Secondary endpoints: The frequency and nature of adverse events

Exploratory endpoints:

- to assess the in vitro susceptibility of *P. falciparum* isolates to dihydroartemisinin, piperaquine, artesunate and mefloquine at D0 and Day of recrudescence;
- to determine the polymorphism of molecular markers of *Plasmodium falciparum* and Kelch gene

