Name(s) of antimalarial drug(s)	Time of dose (hh:min)	Number of tablets	Did the patient vomit?	Time of vomiting (hh:min)
			 Yes  No	
			 Yes  No	
Name(s) of other medicine(s)				
			 Yes  No	
			 Yes  No	

Case report form: follow-up day 7

Study number:

Patient identity number:

Date of visit (dd-mm-yyyy):

Clinical status

Presence of danger signs or signs of severe or complicated malaria? Yes No

History of fever within previous 24 h? Yes No

Temperature: °C Axillary

Thick blood smears for estimation of *P. falciparum* parasite counts

Average number of asexual *P. falciparum* parasites/ μ l:

Presence of *P. falciparum* gametocytes? Yes No

Were species other than *P. falciparum* present? Yes No

If yes, which species? *P. vivax* *P. ovale* *P. malariae*

Has a blood sample for PCR been collected? Yes No

Adverse events

Presence of an adverse event? Yes No

If yes, name the adverse event:

Is it a serious adverse event? Yes No. If yes, inform the sponsor.

Medication administration

Name(s) of antimalarial drug(s)	Time of dose (hh:min)	Number of tablets	Did the patient vomit?	Time of vomiting (hh:min)
			 Yes  No	
			 Yes  No	
Name(s) of other medicine(s)				
			 Yes  No	
			 Yes  No	

Case report form: follow-up day 14

Study number:

Patient identity number:

Date of visit (dd-mm-yyyy):

Clinical status

Presence of danger signs or signs of severe or complicated malaria? Yes No

History of fever within previous 24 h? Yes No

Temperature: °C Axillary

Thick blood smears for estimation of *P. falciparum* parasite counts

Average number of asexual *P. falciparum* parasites/μl:

Presence of *P. falciparum* gametocytes? Yes No

Were species other than *P. falciparum* present? Yes No

If yes, which species? *P. vivax* *P. ovale* *P. malariae*

Has a blood sample for PCR been collected? Yes No

Adverse events

Presence of an adverse event? Yes No

If yes, name the adverse event:

Is it a serious adverse event? Yes No. If yes, inform the sponsor.

Medication administration

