If the patient is pregnant, follow-up of the pregnancy is required, including: clinical examination of the infant at birth and 6-8 weeks after birth. Please provide comments below. If needed fill in the serious adverse event report form):

Case report form: final day of follow-up day 42

Overall assessment

Outcome:

- adequate clinical and parasitological response
- early treatment failure
- late clinical failure
- late parasitological failure
- lost to follow-up
- withdrawn (complete section below: Reason for withdrawal)

Outcome occurred on follow-up day: (e.g. 1, 2, 3, 7, 14, ...)

PCR:

- P. falciparum* recrudescence
- P. falciparum* reinfection
- other species
- mixed with *P. falciparum* recrudescence
- mixed with *P. falciparum* reinfection
- unknown

PCR corrected results:

- adequate clinical and parasitological response
- early treatment failure
- late clinical failure
- late parasitological failure
- lost to follow-up
- withdrawn

Reason for withdrawal:

Other comments:

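### The screening and day-0 forms admit only P. falciparum, and no form records P. vivax density, although P. vivax is half the planned sample

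*Protocol*

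**What the plan says.** The body of the protocol plans for two species. The synopsis gives "Sample Size: 600 (120 in one site: 60 *P. falciparum* cases and 60 patients *P. vivax* cases", section 2 makes efficacy against both species a primary objective, and section 3.5 admits "mono-infection with *P. falciparum* or *P. vivax* by microscopy".

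The forms plan for one. The inclusion list in Appendix 5 has "mono-infection with P. falciparum confirmed by positive blood smear (i.e. no mixed infection" and states that a patient who does not meet every item is not eligible. The same form asks "Were species other than P. falciparum present" and makes a yes answer disqualifying. It has a tick box for P. vivax among the species, but nothing on the form makes such a patient eligible. The day-0 page in Appendix 7 repeats the other-species question with the same consequence.

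On the day-0 and follow-up pages of Appendix 7 the only density field is "Average number of asexual *P. falciparum* parasites". Any other species gets a yes/no answer and its name. The outcome page is headed "Case report form: final day of follow-up day 42", while section 3.1 follows P. vivax patients for 28 days.

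On age, the form says "age between 2 and 60 years" without regard to drug. Section 3.5 says "For those receiving ASMQ: age between 18 and 60 years", and sections 3.3 and 3.6 agree with it.

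**The concern.** These forms are not illustrative. Section 6.1 says the Appendix 5 form will be used at screening, section 6.2 says the same of the Appendix 7 form for enrolled patients, and section 7 has clinical and laboratory data entered on the case report form daily. Staff therefore have two incompatible instructions on which species to enrol, and different sites could resolve the conflict differently. At stake is either the whole P. vivax part of the primary objective or, if P. vivax patients are enrolled regardless, the data behind part of the outcome classification. A later analysis plan can redefine an analysis, but it cannot recover densities that never reached the study record.

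**Working it through.** **Planned numbers.** Inputs from section 8.1: failure rate 10%, precision 8 percentage points, 95% confidence, 10% allowance for losses.

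- n = 1.96² × 0.10 × 0.90 / 0.08² = 54.02; the protocol states 54.
- 54 / (1 − 0.10) = 60; alternatively 54 × 1.10 = 59.4, rounded up to 60. The protocol states 60.
- Per species: 5 sites × 60 = 300. Total: 300 + 300 = 600. P. vivax share: 300 / 600 = 50%.

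The stated figures reproduce, and nothing in this point alters them.

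**Body against forms.**

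| Item | Body of the protocol | Forms |
|---|---|---|
| Eligible species | Either species alone (3.5) | P. falciparum alone; any other species disqualifies (Appendix 5; stop repeated on the day-0 page) |
| Density | Asexual parasites counted on every film, not limited to one species (5.2.4) | P. falciparum field only |
| End of follow-up | Day 42 for P. falciparum, day 28 for P. vivax (3.1, 3.7) | Outcome page headed day 42 |
| Age | 2–60 for ASP, 18–60 for ASMQ (3.3, 3.5, 3.6) | 2–60 for everyone |

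**If the forms are obeyed.** A P. vivax mono-infection fails the species item and triggers the other-species stop. Number passing: 0 of 300. Enrolment is limited to the 300 P. falciparum patients, and there is no P. vivax efficacy estimate.

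**If section 3.5 is obeyed.** Take the four early-failure criteria in Appendix 4 in turn for a P. vivax patient:

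1. Danger signs or severe malaria with parasites on days 1–3: needs presence only, so it can be evaluated.
2. Day-2 count above the day-0 count: needs two densities, so it cannot be evaluated if the patient is positive on day 2.
3. Parasites on day 3 with temperature of at least 37.5 °C: needs presence and temperature, so it can be evaluated.
4. Day-3 count at least 25% of the day-0 count: needs two densities, so it cannot be evaluated if the patient is positive on day 3. A patient who is also febrile on day 3 has already failed under criterion 3.

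A patient negative on both days is cleared on criteria 2 and 4 without any density. For a patient still positive, early failure may be impossible to rule out. An adequate response then cannot be confirmed either, because it requires that no failure criterion was met earlier. Late clinical and late parasitological failure need only presence of parasites, temperature, danger signs or fever history, all of which the forms capture.

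**Age.** The form's exclusion list has no age item, so nothing on it stops an otherwise eligible P. falciparum patient aged 2–17 at one of the three ASMQ sites. Section 3.8 then classes that patient as an erroneous inclusion: withdrawn, with no outcome assigned.

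**The case against.** The best defence is that the intention is not in doubt. The synopsis, objectives, eligibility criteria and sample size all include P. vivax, and section 6.1 requires all enrolment criteria to be met, so trained staff would probably follow the body of the protocol. Section 5.2.4 also has densities counted on all slides by two microscopists, so the measurement is planned and only a place to write it is missing. That is right as to intent, and it is why this is an inconsistency in the forms rather than a decision to exclude P. vivax. It does not remove the conflict: following the body means overriding an explicit ineligibility instruction, and writing P. vivax counts in a field labelled for P. falciparum is improvisation that may differ by site.

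Four stronger readings are tempting and are not supported:

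- That P. vivax patients cannot be classified at all. The outcome list on the final page is neutral as to species, and late failures and two of the four early-failure criteria need no count.
- That all 300 are both turned away and misclassified. These are alternatives, and the second touches only patients still positive on day 2 or day 3.
- That the outcome page offers only P. falciparum PCR categories. It also lists other species and unknown, and has a field for the day on which the outcome occurred. PCR correction is planned for P. falciparum only (sections 2 and 3.1), so a block built around that species is expected.
- That every patient aged 2–17 at an ASMQ site passes the form. The form's own species stop rejects those with P. vivax, and the remaining criteria still apply.

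**Conclusion.** The point stands and should be settled before first enrolment. The screening and day-0 forms contradict section 3.5 on species. Applied literally, they exclude 300 of 600 planned patients. If section 3.5 is followed instead, two of four early-failure criteria lack recorded data for P. vivax patients still parasitaemic on day 2 or day 3. The protocol gives no figure for how many that would be; it could be anywhere from 0 to 300. The age mismatch is real but smaller. It concerns otherwise eligible P. falciparum patients aged 2–17 at three sites, and their number is not given either. The day-42 heading on the outcome page is a labelling fault.

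The conclusion assumes that the appended forms are the ones to be used, as sections 6.1 and 6.2 say, and that no separate P. vivax set exists; the protocol mentions none.

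**What to change.** - Add an enrolled-species field (P. falciparum or P. vivax) to the screening form and the case report form.
- Reword the species inclusion item to admit either species alone, and tie the stop rule on the screening and day-0 forms to any species other than the enrolled one. Word the form's exclusion item on other species the same way.
- Make the count fields on the screening, day-0 and all follow-up forms species-specific, so that asexual P. vivax density is recorded.
- Reconcile the form's age line with section 3.5, separately by drug.
- Relabel the outcome page so that it can be completed at day 28 for P. vivax, with the PCR block marked not applicable for those patients.

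The cost is editing the forms and the matching data-entry fields before first enrolment. Section 8.4 requires agreement from the principal investigator, the sponsor and the review boards for changes after acceptance. No extra visit, sample or slide reading is needed, and the sample size stays at 600.
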